### **Cancer treatment**

Cancer treatment options depends on cancer type, stage, and other factor such as age, and general health status of each patient. Treatment is founded in three major strategies: surgery, radiotherapy and chemotherapy. Chemotherapeutic drugs work causing cellular death in diverse ways. Genotoxic agents are drugs that damage DNA, interfere with DNA replication, stop cellular division or induce cellular apoptosis. However, chemotherapeutic drugs also affect non-cancerous cells, contributing to their toxicity. Fast regenerating cells, like the ones from the bone marrow and the walls of the intestines, tend to be more affected, causing neutropenia and mucositis, respectively. Thus, the death of non-cancerous cells constitutes the most frequent adverse reaction of chemotherapy. About 75% of pediatric patients with cancer had suffered at least one adverse reaction associated to chemotherapy,

and 36% had suffered a severe adverse reaction that threatens their life or permanently incapacitates them.

Cisplatin is an irreplaceable drug in the treatment of diverse solid tumors in both adults and children. At the Hospital Infantil de México Federico Gómez, chemotherapeutic schemes that include cisplatin as a first line treatment for solid tumors like osteosarcomas, hepatoblastomas and germ cells tumors.

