### **Safety of magnesium supplementation**

Adverse effects of magnesium caused by ingestion of food hadn't been identified since kidneys have mechanisms for the elimination of magnesium surplus. Nonetheless, adverse effects of magnesium secondary to the ingestion of supplements had been showed. The first symptoms of magnesium surplus are diarrhea and laxative effects that originates on the osmotic activity of non-absorbed salts in the intestine and colon, as well as gastric motility stimulation (these adverse effects are the reason why magnesium salts are used as laxative therapy). Magnesium salts that were reported for diarrhea are carbonate, chloride, gluconate and magnesium oxide.

Toxicity symptoms of magnesium surplus manifests when serum concentrations are above 4.2 mg/dL; and can include hypotension, nausea, vomit, facial blush, urine retention, ileus, depression and lethargy before it progresses to muscular weakness, dyspnea, extreme hypotension, irregular heart rhythm and cardiac arrest.

Individuals with renal impair are in major risks to present adverse effects secondary to magnesium supplementation. Symptoms of toxicity induced by magnesium had been observed in patients with renal impair that consumed moderate doses of magnesium laxatives or antacids.

Within clinical trials designed specifically to reduce incidence of hypomagnesemia induced by cisplatin using any magnesium salt it has been described the presence of vomit and diarrhea. However, one of the trials showed no gastrointestinal toxicity.

The Food and Nutrition Board of the US (FNB) established a maximum daily limit for magnesium supplementation in children: from 1 to 3 years, 65mg per day; from 4 to 8 years, 110 mg per day; and in children >9 years, 350 mg per day.

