To evaluate if oral supplementation with magnesium reduces secondary to CBC hypomagnesemia's, serum magnesium will be quantified before CBC and it will be measured again after the apparition of febrile neutropenia or at the moment the patients returns to another CBC cycle. Serum concentrations of magnesium below  $1.6\text{ mg/dL}$  will be considered as hypomagnesemia.

Daily maximum intake of magnesium supplements recommended for children over 9 years is  $350\text{ mg}$ . Nevertheless, the dose that will be used on this protocol is less that the recommended, it is necessary to evaluate safety of supplementation with magnesium in pediatric patients with cancer. To fulfill this purpose, each patient will be given a binnacle where they will register adverse effects that could be presented, such as diarrhea, nausea, vomit, etc.; binnacle is showed in Appendix 1. Moreover, clinical studies like hematic biometry, and other biochemical tests will be performed to determine if there is hepatotoxicity (ALT, AST and alkaline phosphatase), nephrotoxicity (creatinine) and cardiotoxicity (LDH). Biochemical determination will be made on both groups at the basal status and before every CBC cycle. Oral supplementation with magnesium will be interrupted in patients that present severe adverse reactions. All adverse reactions will be registered according NOM-220-SSA1-2015.

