**HOSPITAL INFANTIL DE MÉXICO FEDERICO GÓMEZ**  
**FACULTAD DE ESTUDIOS SUPERIORES ZARAGOZA**

### Daily binnacle of symptoms

Folio \_\_\_\_\_ Delivery of binnacle \_\_\_\_\_

Symptoms	Start Date	Due Date
Constipation		
Diarrhea		
Gas or abdominal distension		
Dizziness		
Nervousness		
Abdominal pain		
Blisters		
Rash		
Itchiness		
Urticaria		
Swelling of eyes, face, lips, tongue, throat, arms, hands, legs, feet, ankles or calfs		
Difficulty breathing or swallowing		
Indigestion		
Excessive fatigue		
Pain on the upper right abdomen		
Nausea		
Loss of appetite		
Yellowing on the skin and eyes		
Flu symptoms		
Paleness		
Fast heartbeat		
Weightloss		
Back pain		
Difficulty or pain to urinate		
Blurry vision, changes on color perception and other visual problems		
Red eyes		
Neck stiffness		
Headache		
Confussion		
Other		

Reception: \_\_\_\_\_

## Appendix 2

HOSPITAL INFANTIL DE MÉXICO FEDERICO GÓMEZ  
FACULTAD DE ESTUDIOS SUPERIORES ZARAGOZA

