**Other adverse effects to chemotherapy**

Adverse effect	Apparition and remission date	Evidence	Treatment	Complications
----------------	-------------------------------	----------	-----------	---------------

---

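### The safety forms have no vomiting row, no severity grade and no field for an early tablet stop, so on their own they cannot give vomiting reliably, severe reactions by arm, or toxicity stops

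*Combined protocol and SAP*

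**What the plan says.** Safety of the supplement is a secondary objective (section 5). Section 6 (Procedure) sets out how it is observed:

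- **Diary, Appendix 1.** "each patient will be given a binnacle where they will register adverse effects that could be presented, such as diarrhea, nausea, vomit, etc".
- **Stop rule.** "Oral supplementation with magnesium will be interrupted in patients that present severe adverse reactions". This is the only stop for toxicity. The planned stops are an episode of febrile neutropenia (FN) or return for the next cisplatin cycle.
- **Registration.** "All adverse reactions will be registered according NOM-220-SSA1-2015". The standard is cited as reference 52; its content is not reproduced.
- **Laboratory tests.** Blood count, liver enzymes, creatinine and LDH.

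Section 2 (Safety of magnesium supplementation) puts vomiting among the symptoms of magnesium excess, which "can include hypotension, nausea, vomit, facial blush, urine retention, ileus, depression and lethargy". Of earlier trials of magnesium against cisplatin-induced hypomagnesemia it says "it has been described the presence of vomit and diarrhea", and adds that one trial saw no gastrointestinal toxicity.

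Section 7 plans an intention-to-treat analysis and a per-protocol analysis restricted to patients who finish the protocol. It describes no analysis of adverse events.

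**The concern.** The forms do not collect some of what the text relies on. The stop rule depends on severity, but the symptom forms do not record it. The text expects vomiting in the diary, but the diary does not prompt for it. A child may stop tablets early because of a reaction, but no field says when or why.

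What is at stake is the safety objective. Both arms receive cisplatin-based chemotherapy, so an ungraded count of nausea or diarrhea will consist largely of whatever chemotherapy causes. A severe reaction would look the same as a mild one on the diary. Data that a form never asked for cannot be recovered reliably at analysis. There is a smaller consequence for efficacy: if an early stop affects who is judged to have finished, membership of the per-protocol set rests on information with no assigned place.

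**Working it through.** **1. Text against forms.**

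| Item needed | Where the text calls for it | Appendix 1 diary | Appendix 2 capture sheet |
|---|---|---|---|
| Vomiting | Named in Procedure; background lists it twice | 29 named rows, including nausea, none for vomiting; only *Other* | Only as a free entry in the adverse-effect table |
| Severity | Stop rule | Columns are symptom, start date and due date | Columns are effect, dates, evidence, treatment and complications |
| Early tablet stop, date and reason | Stop rule; per-protocol set | None | No dedicated field; free text or *Comments* |

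The diary headed "Daily binnacle of symptoms" and the capture-sheet table with the column "Apparition and remission date" both have complete-looking headers, so the gap does not appear to come from the PDF reading. Appendix 3 defines no adverse-event or tablet-stop variable. The planned stops can be dated, from the FN date or from the date of the laboratory measurement after supplementation. A stop for a reaction cannot.

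**2. Is severe defined elsewhere?** The nearest wording is in section 2 (Cancer treatment): "36% had suffered a severe adverse reaction that threatens their life or permanently incapacitates them". That is a background figure per patient for chemotherapy. It is not written as a threshold for stopping tablets.

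**3. Denominator.** The plan's 107 cycles per group reproduces. With 62% against 42%, two-sided alpha 0.05 and 80% power, n = [1.960 × √(2 × 0.52 × 0.48) + 0.842 × √(0.62 × 0.38 + 0.42 × 0.58)]² / 0.20² = 96.8. The continuity correction gives (96.8/4) × [1 + √(1 + 4/(96.8 × 0.20))]² = 106.5, rounded up to 107.

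**4. Expected numbers.** No severe-reaction rate is given. Assume 2% to 5% of supplemented cycles: 107 × 0.02 = 2.1 and 107 × 0.05 = 5.4, so about 2 to 5 cycles. Because the only toxicity stop is for severe reactions, about the same number would stop early. The number could be near zero, given the earlier trial with no gastrointestinal toxicity. It could also be higher, since the rule is not limited to reactions attributed to the tablets.

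**5. What ungraded counts can show.** Assume a common symptom is recorded in a proportion p of cycles in each arm. The 95% half-width of the arm difference is 1.96 × √(2p(1−p)/107): 12.3 points at p = 0.30, 13.4 at 0.50 and 13.1 at 0.60. An excess of 2 to 5 points in severe reactions would not be visible.

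**6. What graded counts can show, on the same two-arm basis.**

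- 2/107 against 0/107: Fisher's exact p = 0.50.
- 5/107 against 0/107: Fisher's exact p = 0.06.
- If severe chemotherapy reactions occur in 5% or 10% of control cycles (assumption) and the excess is 5 points, the half-width is 1.96 × √[(0.05 × 0.95 + 0.10 × 0.90)/107] = 7.0 points, or 1.96 × √[(0.10 × 0.90 + 0.15 × 0.85)/107] = 8.8 points.

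Grading therefore would not reliably show a 2 to 5 point excess either. It would give a count with an interval: 2/107 = 1.9% (exact 95% CI 0.2% to 6.6%), or 5/107 = 4.7% (1.5% to 10.6%). All these figures treat cycles as independent. A child may contribute several, so they are approximate.

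**The case against.** The strongest objection is that the plan does not rely on these two forms alone. All reactions are to be registered under the pharmacovigilance standard, and that registration may record severity. This stands: a reader might infer that the trial will hold no severity data, and the documents do not support that. They show only that the trial's own symptom forms lack it, and that no text links the registration to the stop rule or to a comparison by arm.

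Second, vomiting fits under *Other*, seriousness can be partly inferred from the treatment and complications columns, and a stop can be written under *Comments*. That is so, and vomiting is not lost altogether. But an unprompted entry is weaker than a named row, particularly for an effect that the protocol itself expects to see in the diary.

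Third, severe counts mix chemotherapy and tablet effects just as ungraded counts do, and the trial is open-label, so severity rated by families could differ between arms through expectation. Both points stand. The first limits what grading can show. The second is a reason to have study staff assign the grade.

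Fourth, the dose is below the 350 mg daily limit, the trial is classed as minimum risk, and severe reactions may be very few. This bears on priority. It does not remove the mismatch between text and forms.

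**Conclusion.** The point holds as a gap in safety recording. The trial forms alone cannot give vomiting reliably, severe reactions by arm, or the number and timing of toxicity stops. Free text, *Comments* and the external registration may recover some of this; how much cannot be judged from the documents.

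The affected number is probably small: about 2 to 5 of 107 supplemented cycles under an assumed rate of 2% to 5%, which has no source in the documents. The finding does not depend on that rate, because the missing fields are established by reading the forms.

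Two stronger readings are not supported. A reader might infer that the FN result is compromised. The intention-to-treat analysis counts every assigned cycle whether or not tablets were stopped, so it is unaffected; only the per-protocol set may depend on early stops. A reader might also infer that grading would let the trial detect a small excess of severe reactions. Step 6 of the working shows that it would not.

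This is a cheap improvement of minor priority.

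**What to change.** 1. **Appendix 1:** add a row for vomiting.
2. **Appendix 2:** add a CTCAE v4.0 grade (already cited as reference 50) for each adverse effect, assigned by study staff in both arms. For the supplemented arm, add the tablet stop date and the reason.
3. **Section 6 (Procedure):** state which grade triggers the stop. The choice of threshold is the sponsor's.
4. **Section 7:** report graded events by arm, and toxicity stops in the supplemented arm, descriptively. State whether a cycle stopped early for toxicity counts as finishing for the per-protocol analysis.

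The cost is slightly longer forms, a little grading work by staff, and revision of documents that the committees have already accepted. No visit or assay is added.

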## 7. Analysis data plan

Continuous variables with normal distribution will present as means and standard deviation. If variable have free distribution they will be presented as median and interquartile ranges. Categorical variables will be presented as frequencies and percentages. Operability of variables is showed at Appendix 3. Statistic differences at basal status will be calculated through t-Student test for continuous variables, whilst qualitative variables will be contrasted by  $\chi^2$  test. A  $p < 0.05$  will be considered as statistical significance.

Proportion of patients with febrile neutropenia will be calculated in both groups means the division of number of cases with febrile neutropenia between the total of CBC cycles assigned to each group (experimental or control). Efficacy of supplementation with magnesium will be determined through calculation of Relative Risks with Confidence Interval of 95% (CI 95%). Relative Risks will be considered significant when the value of CI95% don't cross the unit. Furthermore, Absolute Risk Reduction and Number Needed to Treat will be calculated. To adjust principal confounding variables, a Multivariate Analysis will be made with a Multiple Logistic Regression. Analysis by protocol (just patients that finish protocol) and by intention to treat (including all patients) will be made. Statistical analysis will be made performed with SPSS software v.21 (Chicago, IL, US).

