### *Procedure*

Basal status of trial will be integrated at the moment the attending physician indicates that the patient will be treated with cisplatin-based chemotherapy (CBC). The clinical monitor will establish contact with the parent of the patient and explain the purpose of the trial and will invite them to participate through signing the informed consent. Once the informed consent is signed the clinical monitor will explain the patient the purpose of the trial in order to obtain the informed assent.

To prove the hypothesis, it is required to randomize 107 CBC cycles to the intervention group and 107 CBC cycles to the control group. To determine whether the patient will receive supplementation or not in that CBC cycle, the clinical monitor will notify the principal investigator that a patient will commence treatment. In response the investigator will communicate the clinical monitor where to allocate the patient's CBC cycle. Randomize will be made by generating non-repeated random numbers with the program available at: <http://randomnumbregenerator.intemodino.com/es/generador-de-numeros-aleatorios.html>.

Patients assigned to the supplementation group will receive institutional care protocol plus a bottle with magnesium oxide tablets and will be explained that they should take a tablet daily. In the case that the patients were assigned to the control group they will receive institutional care protocol only.

Oral supplementation with magnesium consists on a daily tablet (245 mg magnesium oxide and 5mg magnesium gluconate, GNC, US). Supplementation will be interrupted when the patients returns for the administration of another cisplatin cycle or with the appearance of a febrile neutropenia episode. In the same sense, patients on control group will be monitored until an FN episode appears or until they return for the next cisplatin cycle.

The main outcome of this study is the apparition of febrile neutropenia that is defined as a neutrophils total count below  $1000/\text{mm}^3$  together with a unique temperature  $>38.3\text{ }^\circ\text{C}$  or a sustained temperature of  $\geq 38\text{ }^\circ\text{C}$  for over an hour. Patients with a neutrophils total count  $<100/\text{mm}^3$  will be considerate as a profound neutropenia. Clinical monitor will visit the emergency department every day to identify if one of the enrolled patients has been hospitalized due febrile neutropenia diagnosis.

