### *Sample Size Calculation*

Necessary number of patients was estimated considering a normal distribution means two proportions formula, using  $\alpha = 0.05$  (two tails),  $\beta = 0.20$ , 1 on 1 proportion of assignment to each group. For calculus it was considered that non-exposed group will have a proportion of 62%, while supplemented group will have a proportion of 42% (delta

20%). With the previous conditions and considering a continuity correction, to perform the study it is required to randomize 214 cycles and assign 107 to control group and 107 to supplemented group. Calculus was done with Sample Size Calculator for Designing Clinical Research by University of California San Francisco, available at <http://www.sample-size.net/sample-size-proportions/>.

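### CBC cycles are analysed as independent observations, yet the plan never says whether, or how, a child may contribute more than one cycle

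*Combined protocol and SAP*

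**What the plan says.** **Analysis (Section 7).** The primary proportion is labelled as one of patients: "Proportion of patients with febrile neutropenia will be calculated in both groups". It is computed as the "number of cases with febrile neutropenia between the total of CBC cycles assigned to each group (experimental or control"). Efficacy is declared when the 95% CI of the relative risk excludes 1. For adjustment, "a Multivariate Analysis will be made with a Multiple Logistic Regression". No robust variance, patient effect or other method for repeated cycles is named. The analysis sets are described by patient: "Analysis by protocol (just patients that finish protocol) and by intention to treat (including all patients) will be made".

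**Sample size (Section 7, Sample Size Calculation).** The paragraph opens by speaking of a number of patients and ends with cycles: "it is required to randomize 214 cycles and assign 107 to control group and 107 to supplemented group".

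**Allocation (Section 6, Procedure).** The aim is "To determine whether the patient will receive supplementation or not in that CBC cycle", and the investigator "will communicate the clinical monitor where to allocate the patient's CBC cycle". The trigger is that "the clinical monitor will notify the principal investigator that a patient will commence treatment". The Abstract (Materials and Methods) instead says that children are randomised, and both the Abstract and Study Design describe parallel groups.

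**Return for further cycles (Section 6, Procedure).** Follow-up runs to febrile neutropenia (FN) or to the child's return for the next cisplatin cycle, and biochemistry is repeated before every cycle. No inclusion, non-inclusion or exclusion criterion restricts a child to one randomised cycle.

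**The concern.** An ordinary relative-risk interval and an ordinary logistic regression treat each cycle as a separate, independent unit. Two cycles from one child share the tumour, the chemotherapy scheme, renal function and marrow reserve, so their FN outcomes are likely to be correlated. Whether that correlation matters depends on how a child's later cycles are allocated, and the plan does not say.

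Two things are at stake. One is the error rate of the rule that declares efficacy. The other is the definition of the analysis sets: if cycles are allocated separately, one child may hold cycles in both arms, and a set described by patient does not say how those cycles are handled.

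**Working it through.** **1. The plan's own figure.** Inputs from the Sample Size Calculation: 62% against 42%, two-sided alpha 0.05, power 80%, 1:1, continuity correction. The mean proportion is 0.52.

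n = [1.960 × √(2 × 0.52 × 0.48) + 0.842 × √(0.62 × 0.38 + 0.42 × 0.58)]² / 0.20² = (1.385 + 0.583)² / 0.04 = 96.8 per arm.

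With the correction: (96.8/4) × [1 + √(1 + 4/(96.8 × 0.20))]² = 106.5, so 107. The plan's figure is reproduced and is right for independent observations.

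Power at 107 per arm without the correction, which is the closer match to the planned relative-risk interval: Φ[(0.20 × √107 − 1.385)/0.692] = Φ(0.988) = 83.8%. With the correction it is 80.2%.

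**2. One cycle per child.** Nothing changes. Simulating the planned log-RR interval with independent outcomes gave a type I error of 4.5%.

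**3. A child's cycles all in one arm.** Let m be cycles per child and ICC the within-child correlation. Both are assumed, m from 2 to 6 and ICC from 0.05 to 0.3. With 214 cycles this means about 214/6 = 36 to 214/2 = 107 children.

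- Design effect: DE = 1 + (m − 1) × ICC
- Effective cycles per arm: 107/DE
- Type I error of the planned interval: 2 × [1 − Φ(1.960/√DE)]
- Power of a valid uncorrected test: the formula in step 1 with 107/DE in place of 107

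| m | ICC | DE | Effective n per arm | Type I, formula | Type I, simulated | Valid power |
|---|---|---|---|---|---|---|
| 2 | 0.05 | 1.05 | 101.9 | 5.6% | 5.1% | 82.0% |
| 2 | 0.10 | 1.10 | 97.3 | 6.2% | 5.9% | 80.2% |
| 2 | 0.30 | 1.30 | 82.3 | 8.6% | 8.2% | 73.3% |
| 3 | 0.30 | 1.60 | 66.9 | 12.1% | 11.5% | 64.1% |
| 4 | 0.20 | 1.60 | 66.9 | 12.1% | 11.6% | 64.1% |
| 6 | 0.30 | 2.50 | 42.8 | 21.5% | 21.2% | 45.6% |

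The simulations used beta-binomial outcomes with 62% FN in both arms (20,000 replicates for the first row, 40,000 for the others).

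**4. Each cycle freshly randomised, effect common to all children.** Over m = 2 to 6 and ICC 0.1 to 0.3, the planned interval had a type I error of 4.4% to 5.0% and power of about 83% to 84% (8,000 replicates). This is about nominal.

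**5. Each cycle freshly randomised, effect varying between children.** With an assumed standard deviation of 0.5 to 1.0 for the effect on a latent probit scale, ICC 0.2 and m = 4 or 6, coverage was 94.1% down to 90.2% (6,000 replicates). The interval is somewhat too narrow.

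**6. A child's cycles split evenly between arms.** At m = 2 or 4 and ICC 0.1 or 0.3, coverage was 95.9% to 98.2% (6,000 replicates). The interval is too wide.

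**7. Does clustering on the child repair it?** An exchangeable Poisson GEE was simulated at (m, ICC) = (2, 0.1), (2, 0.3), (4, 0.2) and (6, 0.3), with 1,500 replicates each. With a child's cycles in one arm, type I error was 4.3% to 5.8% with the ordinary robust SE and 3.8% to 4.7% with a small-sample correction. With fresh randomisation and the corrected SE it was 3.5% to 5.1%. Monte Carlo error is about 1 point either way (1.96 × √(0.05 × 0.95/1500) = 1.1 points), so this is supportive, not a proof for every design.

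**The case against.** The operative text favours allocation by cycle: Procedure allocates the cycle, Section 7 counts cycles assigned, and the sample size randomises cycles. The main text for allocation by child is one sentence in the Abstract. Under fresh randomisation with a common effect, the planned interval performs about as intended. This stands, and it makes the inflation in step 3 conditional.

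There is also evidence that each child enters once. Allocation is requested when a patient is about to start treatment, follow-up ends at FN or the next cycle, and hypomagnesemia before CBC bars inclusion. The capture sheet (Appendix 2) has one before-and-after pair of columns and one FN block, but that would equally fit one sheet per cycle. None of this amounts to a one-cycle limit, and the cycle-based wording and sample size leave re-entry open.

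The upper end of the range is extreme: 21% needs every child to contribute six cycles at an ICC of 0.3. At two cycles and an ICC of 0.05, the effect is negligible.

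A reader might infer that the intention-to-treat set cannot be built. That goes too far: every child can be included, with each cycle analysed in its assigned arm. The per-protocol set is the ambiguous one, because finishing the protocol is described for a patient and not for a cycle.

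**Conclusion.** The point holds as a should-fix. What the documents establish is a mixed unit, no re-entry rule, and an analysis with no provision for repeated cycles from one child. The consequence is conditional:

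- **One cycle per child:** no effect.
- **Fresh randomisation of each cycle:** about nominal with a common effect, somewhat too narrow if the effect varies between children.
- **Even split within a child:** interval too wide.
- **Shared arm:** interval too narrow, with type I error of about 5% to 21% and valid power of about 82% down to 46%, against 83.8% for independent cycles.

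The ranges rest on assumed values of cycles per child and ICC, and the fifth step of the working on an assumed spread of effects.

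Two stronger readings are tempting. A reader might infer that the trial's type I error is inflated. The documents do not support that, because they never say that a child's later cycles stay in the first arm. A reader might also infer that the interval is wrong only in that case. That does not hold either, since an even split or an effect that varies between children also moves it from nominal.

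**What to change.** 1. State one unit of allocation throughout, whether a child may re-enter, and how later cycles are allocated. If each child enters once, saying so closes the point.
2. If a child can contribute more than one cycle, compute the intervals for the relative risk, absolute risk reduction and number needed to treat, and the adjusted model, with clustering on the patient folio. GEE with robust standard errors would do. A clustered logistic model keeps the planned adjusted analysis.
3. In that case, also define the intention-to-treat and per-protocol sets by cycle, each in its assigned arm.
4. If a child's cycles stay in one arm, restate the power of 214 cycles with a design effect over a stated range of cycles per child and ICC. This needs no extra enrolment.

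Relabelling the parallel-group design and replacing logistic with Poisson regression are optional.

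**Cost.** Wording and a slightly more complex model. No new data are needed, since the folio is already on the capture sheet. If cycles share an arm, the interval widens and the stated power falls. Under fresh randomisation, the simulated GEE gave power of 83.9%, 85.8% and 89.2% at (2, 0.1), (4, 0.2) and (6, 0.3), against 84.7%, 83.2% and 82.7% for the planned interval, so no material loss was seen. Whether SPSS v.21 offers the small-sample correction was not checked.

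### The only adjusted analysis is a logistic regression, so the plan yields no adjusted version of its own efficacy measures (relative risk, absolute risk reduction, number needed to treat)

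*Combined protocol and SAP*

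**What the plan says.** Section 7 (Analysis data plan) fixes the measure: "Efficacy of supplementation with magnesium will be determined through calculation of Relative Risks with Confidence Interval of 95% (CI 95%). The result counts as significant when that interval excludes 1, and the same paragraph adds the ARR and the NNT.

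The adjusted analysis gets one sentence: "To adjust principal confounding variables, a Multivariate Analysis will be made with a Multiple Logistic Regression". The Abstract names the same model and describes it as adjusting the main variable. Neither place mentions an odds ratio, and neither says how the logistic output is to become an adjusted relative risk, ARR or NNT. The covariates are not named either. Appendix 3 lists candidates such as diagnosis, accumulated cytotoxic doses and G-CSF use, without assigning them to the model.

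The Sample Size Calculation supplies the expected rates: the "non-exposed group will have a proportion of 62" per cent, and the supplemented group 42 per cent.

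**The concern.** The exponentiated coefficient of a logistic model is an odds ratio. It approximates a relative risk only when the outcome is rare, and here about half of all cycles are expected to have the event. Two things follow.

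First, the adjusted result will be on a different scale from the main one, and its point estimate will sit much further from 1 for the same data. The plan asks for the size of the effect as a relative risk, ARR and NNT, and provides no adjusted form of any of them.

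Second, the odds ratio is non-collapsible: conditioning on a prognostic covariate moves it away from 1 even when that covariate is perfectly balanced between arms. The plan presents the model as a correction for confounding. Someone comparing the crude relative risk with the adjusted odds ratio could therefore take a change of scale, plus this shift, for confounding removed.

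**Working it through.** **Inputs.** From the Sample Size Calculation: control risk p1 = 0.62, supplemented risk p2 = 0.42, two-sided alpha 0.05, power 0.80, 1:1 allocation, continuity correction, 107 cycles per arm. The documents state no numerical relative risk or odds ratio; both are derived below.

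**1. The plan's own figure.** With mean risk 0.52:

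n = [1.960 × √(2 × 0.52 × 0.48) + 0.842 × √(0.62 × 0.38 + 0.42 × 0.58)]² / 0.20² = 96.8, so 97 per arm without the correction.

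With the correction: (96.8/4) × [1 + √(1 + 4/(96.8 × 0.20))]² = 106.5, so 107 per arm. The stated size is reproduced, so the rates have been read as the plan uses them.

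**2. The two scales at those rates.**

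- Relative risk = 0.42/0.62 = 0.677, a 32% lower risk.
- Crude odds ratio = (0.42/0.58)/(0.62/0.38) = 0.444, 56% lower odds.
- ARR = 0.62 − 0.42 = 0.20; NNT = 1/0.20 = 5.

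If 0.444 were misread as a relative risk, the supplemented risk would appear to be 0.444 × 0.62 = 27.5% instead of 42%, and the NNT 1/(0.62 − 0.275) = 2.9 instead of 5.

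**3. Strength of evidence on each scale**, if exactly these rates were observed with 107 independent cycles per arm:

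- Log relative risk = −0.389; SE = √[0.38/(107 × 0.62) + 0.58/(107 × 0.42)] = 0.137; z = −2.85, p = 0.0043; 95% CI for the relative risk 0.52 to 0.89.
- Log odds ratio = −0.812; SE = √[1/(107 × 0.62 × 0.38) + 1/(107 × 0.42 × 0.58)] = 0.279; z = −2.91, p = 0.0036; 95% CI for the odds ratio 0.26 to 0.77.

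The point estimates differ widely; the evidence against no effect is almost the same.

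**4. Effect of adjusting for a balanced covariate score.** Assume a normal prognostic score with standard deviation s on the logit scale and the same distribution in both arms. For each s, find the intercepts a1 and a2 at which the average of 1/(1 + exp(−(a + sX))) over X ~ N(0,1) equals 0.62 and 0.42. The conditional odds ratio is exp(a2 − a1). The marginal relative risk is 0.677 in every row.

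| Assumed s | Conditional odds ratio |
|---|---|
| 0 | 0.444 |
| 0.2 | 0.440 |
| 0.3 | 0.436 |
| 0.5 | 0.423 |
| 0.8 | 0.396 |
| 1.0 | 0.375 |
| 1.2 | 0.352 |
| 1.5 | 0.318 |

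The documents give no value for s, so this is a range and not a prediction. There is no confounding in any row; all movement below 0.444 is non-collapsibility.

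**The case against.** The best defence is that nothing in the trial's decision depends on the logistic model. Efficacy is judged on the unadjusted relative risk and its confidence interval, ARR and NNT are planned alongside it, and logistic regression is a standard and valid adjusted test for a binary outcome. The plan nowhere says that the odds ratio will be read as a relative risk. A crude odds ratio printed beside the adjusted one would put both on one scale, and with weak covariates the remaining shift is trivial (0.444 to 0.423 at s = 0.5). All of this stands, and it limits the point to the reporting of the adjusted effect.

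It does not remove the point. A crude odds ratio is not planned, and even if it were added, the trial would still have no adjusted relative risk, ARR or NNT.

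A reader might infer more than the documents support:

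- *That logistic regression is the wrong model or biases the main result.* It does neither: the main result is unadjusted, and the same fit can supply the missing measures.
- *That the adjusted analysis would give stronger evidence.* The comparison of z values on the two crude scales (−2.85 and −2.91) shows that the change of scale adds almost nothing.
- *That the plan sets a target relative risk of 0.68, or that the adjusted odds ratio will be 0.44.* The first figure is derived from the planning rates; the second is the crude odds ratio at those rates.

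**Conclusion.** The point holds as a mismatch of effect scale between the main and adjusted analyses. At the planning rates the gap is a relative risk of 0.68 against a crude odds ratio of 0.44, and it follows from the plan's own figures alone. The further move to between 0.44 and 0.32 rests on an assumed covariate strength (logit SD 0.2 to 1.5); its direction is certain for a balanced prognostic covariate, but its size may be negligible. As written, the adjusted result cannot be set against the crude relative risk to show that confounding was removed.

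The sample size, the primary estimate and the decision rule do not change. The mismatch would exist even if every cycle were independent, so it is separate from how repeated cycles in the same child are handled. The change should be made before analysis, so that the scale of the adjusted result is not chosen after the data are seen.

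**What to change.** Keep the logistic model and add to section 7 what will be reported from it:

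1. For every analysed cycle, predict the risk of febrile neutropenia from the fitted model twice, once as supplemented and once as control, and average each set over all cycles.
2. Report the ratio of the two averages as the adjusted relative risk and their difference as the adjusted ARR, each with a 95% confidence interval (bootstrap or delta method, named in advance). Take the adjusted NNT as the reciprocal of that ARR.
3. Show any odds ratio as supplementary, with a statement that it is not to be read as a relative risk.

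Poisson regression with a log link and robust variance is an alternative for the adjusted relative risk only. Its coefficient gives neither the ARR nor the NNT, which would still need standardised risks. Whatever the plan decides about repeated cycles per child should carry through to these intervals, but that is a separate decision.

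The cost is a few sentences in the plan and a little more analysis work. No new data and no more cycles are needed. The adjusted figure will look less dramatic than an odds ratio would.
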